6.5 Concomitant Therapy

All medication which is considered necessary for the subject's welfare, and which is not expected to interfere with the evaluation of the study drug, may be given at the discretion of the Investigator. All concomitant medications (including start/stop dates, dose frequency,

route of administration and indication) must be recorded in the subject's source documentation, as well as in the appropriate pages of the CRF.

6.5.1 Drug-drug interactions relevant for regorafenib

6.5.1.1 Inhibitors / inducers of CYP3A4

Administration of ketoconazole (400 mg for 18 days), a strong CYP3A4 inhibitor, with a single dose of regorafenib (160 mg on Day 5) resulted in an increase in mean exposure (AUC) of regorafenib of approximately 33%, and a decrease in mean exposure of the active metabolites, M-2 (N-oxide) and M-5 (N-oxide and N-desmethyl), of approximately 90%. **It is recommended to avoid concomitant use of strong inhibitors of CYP3A4 activity (Appendix 10.6) as their influence on the steady-state exposure of regorafenib and its metabolites has not been studied.**

Administration of rifampicin (600 mg for 9 days), a strong CYP3A4 inducer, with a single dose of regorafenib (160 mg on Day 7) resulted in a reduction in AUC of regorafenib of approximately 50%, a 3- to 4-fold increase in mean exposure of the active metabolite M-5, and no change in exposure of active metabolite M-2. Other CYP3A4 inducers (Appendix 10.6) may also increase metabolism of regorafenib. **Inducers of CYP3A4 should be avoided, or selection of an alternate concomitant medicinal product, with no or minimal potential to induce CYP3A4 should be considered.**

Appendix 10.6 provides an overview of the most commonly used strong CYP3A4 inhibitors and CYP3A4 inducers) that should be avoided during the study.

6.5.1.2 UGT1A1 and UGT1A9 substrates

In vitro data indicate that regorafenib as well as its active metabolites M-2 inhibit glucuronidation mediated by UGT1A1 and UGT1A9 whereas M-5 only inhibits UGT1A1 at concentrations which are achieved in vivo at steady state.

Administration of regorafenib with a 5-day break prior to administration of irinotecan resulted in an increase of approximately 44% in mean exposure (AUC) of SN-38, a substrate of UGT1A1 and an active metabolite of irinotecan. An increase in mean exposure (AUC) of irinotecan of approximately 28% was also observed. This indicates that **co-administration of regorafenib may increase systemic exposure to UGT1A1 and UGT1A9 substrates**. The clinical significance is unknown and is dependent on the substrate.

6.5.1.3 Breast cancer resistance protein and P-glycoprotein substrates

Administration of regorafenib (160 mg for 14 days) prior to administration of a single dose of rosuvastatin (5 mg), a breast cancer resistance protein (BCRP) substrate, resulted in a 3.9-fold increase in mean exposure (AUC) of rosuvastatin and a 4.6-fold increase in C_{max} . This indicates that co-administration of regorafenib may increase the plasma concentrations of other concomitant BCRP substrates (e.g. methotrexate, fluvastatin, atorvastatin). **Therefore, it is recommended to monitor patients closely for signs and symptoms of increased exposure to BCRP substrates.**

6.5.1.4 CYP isoform-selective substrates

A cytochrome P450 enzyme (CYP) probe substrate study in cancer patients was conducted to evaluate the effect of regorafenib on the pharmacokinetics of CYP2C9 substrate warfarin (10 mg), CYP2C19 substrate omeprazole (40 mg), CYP3A4 substrate midazolam (2 mg) and

CYP2C8 substrate rosiglitazone (4 mg) and to provide information about potential changes in exposure of these substrates when administered with regorafenib.

Overall, the PK data suggest that **regorafenib may be given concomitantly with substrates of CYP3A4, CYP2C8, CYP2C9, and CYP2C19 without the expectation of a clinically meaningful drug interaction.**

6.5.1.5 Antibiotics

The concentration-time profile indicates that regorafenib and its metabolites may undergo enterohepatic circulation. Co-administration with neomycin, a poorly absorbed antimicrobial agent used for eradicating the gastrointestinal microflora (which may interfere with the enterohepatic circulation of regorafenib) had no effect on the regorafenib exposure. There was an approximately 80% decrease in the exposure of the active metabolites M-2 and M-5. Effects of other antibiotics have not been studied. **The clinical significance of the neomycin effect and potential interactions with other antibiotics is unknown, but may result in a decreased efficacy of regorafenib.**

6.5.1.6 Bile salt-sequestering agents

Bile salt-sequestering agents may interact with regorafenib by forming insoluble complexes which may impact absorption (or reabsorption), thus resulting in potentially decreased exposure. **The clinical significance of these potential interactions is unknown, but may result in a decreased efficacy of regorafenib.**

6.5.2 Permitted concomitant therapies

All concomitant medications (including start / stop dates, total daily dose, and indication) must be recorded in the patient's source documentation and in the eCRF.

- Treatment with non-conventional therapies (e.g. herbs or acupuncture) and vitamin/mineral supplements is acceptable provided that they do not interfere with the study endpoints, in the opinion of the investigator. However, **St John's Wort (herbal preparation based on the plant species hypericum) is not permitted.**
- Patients who are therapeutically treated with an agent such as warfarin or heparin or novel oral anticoagulants (NOACs) such as dabigatran or rivaroxaban will be allowed to participate provided that no prior evidence of underlying abnormality in coagulation parameters exists. Close monitoring of at least weekly evaluations for patients on warfarin will be performed until INR is stable based on a measurement that is pre-dose as defined by the local standard of care.
- P-glycoprotein substrates: clinical data indicate that regorafenib has no effect on digoxin pharmacokinetics, therefore can be given concomitantly with p-glycoprotein substrates, such as digoxin, without a clinically meaningful drug interaction (see Section 6.5.1.3).
- Patients may receive palliative or supportive care for any underlying illness (e.g., Megestrol acetate (Megace®) as supportive care).
- Palliative and supportive care for the other disease-related symptoms and for toxicity associated with treatment will be offered to all patients on this trial. The use of anti-diarrheal or anti-emetics according to standard practice is strongly encouraged.
- Bisphosphonates and/or RANKL inhibitor therapies (such as denosumab) for bone metastases may be continued if treatment with an agent from one of these two classes

was initiated prior to signing informed consent. Bisphosphonates and/or RANKL inhibitor therapies cannot be initiated after informed consent has been signed, unless in the opinion of the investigator, the patient does not have PD.

- Radiotherapy:
 - Palliative radiotherapy during the study is allowed for local pain control after individual benefit-risk assessment provided that:
 - In the opinion of the investigator, the patient does not have PD,
 - No more than 25% of the patient's bone marrow is irradiated,
 - The radiation field does not encompass a lung field (to reduce the risk for ILD caused by irradiation pneumonitis).
 - Regorafenib may only be continued during palliative radiotherapy after an individual benefit-risk assessment. The investigator should consult the sponsor.

Note: administration of palliative radiation therapy to a symptomatic solitary lesion or to the brain will be considered clinical progression

- Analgesics.
- Nutritional support.

Major surgery for any reason different than symptom management or tumor control should only be performed during the study period if, in the opinion of the investigator and after careful individual benefit / risk assessment (taking into account the potential wound healing complications that have been described with all anti-VEGF drugs), the surgery will be beneficial for the patient. It is recommended to stop regorafenib treatment two weeks before surgery. The decision to resume regorafenib after surgery should be based on clinical judgment of adequate wound healing. Patients should be placed back on study therapy within 4 weeks of the scheduled interruption of regorafenib.

Note:

- if treatment interruption of regorafenib will be >28 consecutive days - including the 1 week drug holiday - patient must be discontinued from regorafenib.

Patients may receive other medications that the investigator deems to be medically necessary.

6.5.3 Prohibited prior and concomitant therapies

Patients are prohibited from receiving the following therapies during the screening and treatment phase of this trial:

- **Disease-specific anti-neoplastic therapies**, including kinase inhibitors, immunotherapy, chemotherapy, or experimental therapies other than regorafenib are not allowed.
- Surgery for symptom management or tumor control.
- **Strong CYP 3A4 inhibitors / inducers**. Strong CYP3A4 inhibitors or CYP3A4 inducers (See Appendix 10.6) are not allowed.
- Any drug that targets angiogenesis, especially VEGF and VEGFR.

- Tyrosine-kinase inhibitors (TKIs)
- **Antiviral treatment for HCV**
- Bone marrow transplant or stem cell rescue.
- Prior and concomitant palliative radiation therapy is allowed if the target lesion(s) are not included within the radiation field and no more than 25% of the bone marrow is irradiated.
- Use of biologic response modifiers, such as granulocyte colony stimulating factor (G-CSF), within the 3 weeks prior to the randomization date.
 - G-CSF and other hematopoietic growth factors may be used during the study in the management of acute toxicity such as febrile neutropenia when clinically indicated or at the discretion of the investigator; however they may not be substituted for a required dose reduction.
 - Patients taking chronic erythropoietin are permitted.
- Patients taking narrow therapeutic index medications (e.g., warfarin, quinidine, and cyclosporine) should be monitored proactively.
- Investigational anti-tumor agents or anti-neoplastic chemo/hormonal/immunotherapy.

Therapeutic monitoring should be performed consistent with the local clinical standard of care following dose modification of the agent. In general, patients should be closely monitored for side effects of all concomitant medications regardless of path of elimination.

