1.3 Schedule of Activities (SoA)

Table 1-1: Schedule of activities

Procedure	Screening ^a	Intervention Period ^b [Cycles consisting of 4 weeks]		End of study treatment (up to 14 days after last dose)	Safety Follow-up (30-35 days after last dose, phone call)	Notes
		Cycle 1 Day 1 ^c	Cycle 4 Day 1 + every 3 months (+/- 1 week)			
Informed consent	X					
Inclusion and exclusion criteria	X					Including pregnancy test done by treating physician.
Demography	X					
Tumor type	X					
Medical history	X					Medical important events, e.g. Grade 3/4 (S)AEs, since the start of treatment in the feeder study should be reported as medical history in this rollover study.
Study treatment		→→→→→→→→				Recheck clinical status before 1st dose of study medication. Regorafenib dosing as per feeder study protocol.
Drug dispensing		X	X			
Drug accountability		X	X	X		
AE review	X	X	X	X	X	To be documented only: 
 • AEs leading to dose reduction, interruption/delay and discontinuation • Any ongoing Grade 3 and 4 AEs, or Grade 2 AEs that affect vital organs (e.g. heart, liver) per feeder study protocol CTCAE version. These events need to be regraded by the investigator

						according to CTCAE Ver 5.0. • Any new CTCAE Ver 5.0 Grade 3 and 4 AEs, or Grade 2 AEs that affect vital organs (e.g. heart, liver)
SAE review	X	X	X	X	X	To be documented any ongoing or new SAEs
Concomitant medication review	X	X	X	X	X	

Abbreviations: AE - adverse event; CTCAE - Common terminology criteria for adverse events; SAE - serious adverse event.

a During the screening period the participant will be on treatment under the umbrella of the feeder study. At the end of treatment visit of the feeder study, eligibility criteria will be reviewed and the participants should sign informed consent for the rollover study.

b Safety assessments should be done according to local standard of care and regorafenib label information by the treating physician.

c The treating investigator should ensure a seamless transition without a change in the treatment schedule. Any treatment interruption should not exceed 28 consecutive days including 1 week break.

2. Introduction

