4.1 Overall Design

The participants in this open-label program will continue receiving regorafenib monotherapy at the dose level previously assigned under the following conditions:

- as long as the interval of drug interruption does not exceed 4 weeks
- as long as the treating physician feels the participant is continuing to benefit from treatment
- until he/she withdraws consent
- until he/she is non-compliant
- until he/she is lost to follow up
- until an unacceptable toxicity or death occurs
- until patient starts a new anti-cancer treatment
- until the development of a second malignancy

- participants with a beta human chorionic gonadotropin (beta-hCG) test consistent with pregnancy. Pregnancy will be reported along the same timelines as a serious adverse event (SAE).

Prior to receiving study medication for this rollover study, participants will be required to complete at least their EoT visit in their feeder study. During this visit, criteria for the start of a subsequent cycle of therapy, as determined by the guidelines of the feeder protocol (eligibility criteria) will be reviewed and the participants should sign informed consent for the rollover study.

Participants should continue taking study medication dispensed under the umbrella of the feeder studies until first treatment in this rollover study. The participant needs to complete the last treatment cycle in the feeder study and will start treatment in the rollover study at Cycle 1 Day1. The treating investigator should ensure a seamless transition without a change in the treatment schedule. Any treatment interruption should not exceed 28 consecutive days including 1 week break.

Local standards of medical care should be applied to all participants. Details must be recorded in the patient's source documents and may be requested at the discretion of the Sponsor.

The investigator will continuously assess the benefit/risk of regorafenib treatment when the participant is seen in the clinic for his standard of care visits and will ensure that participants that achieve any of the withdrawal conditions above discontinue treatment.

Safety assessments should be done according to local standard of care and regorafenib label information by the treating physician.

Following the EoT assessments from the feeder study, the following information will be recorded in the rollover study eCRF:

- demography including study number, tumor type, and participant's identification number of the feeder study

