6.5.4 Documentation of prior and new concomitant therapies

Any medication or vaccine (including over-the-counter or prescription medicines, vitamins, and/or herbal supplements) that the participant is receiving at the time of enrollment or receives during the study must be recorded along with:

- Reason for use
- Dates of administration including start and end dates
- Dosage information including dose and frequency

The Medical Monitor should be contacted if there are any questions regarding concomitant or prior therapy.

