8.1 Efficacy Assessments

There will be no formal assessments of efficacy during the rollover study.

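### Protocol Sections 6.5.2 and 6.5.3 permit palliative radiotherapy during treatment on different conditions, and the 6.5.3 bullet omits the lung-field safeguard

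*Protocol*

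**What the plan says.** Protocol Section 6.5.2 (Permitted concomitant therapies) has a radiotherapy entry: "Palliative radiotherapy during the study is allowed for local pain control after individual benefit-risk assessment provided that" three conditions are met. They are no PD in the investigator's opinion, at most 25% of bone marrow irradiated, and a lung restriction with its reason given: "The radiation field does not encompass a lung field (to reduce the risk for ILD caused by irradiation pneumonitis". The entry continues: "Regorafenib may only be continued during palliative radiotherapy after an individual benefit-risk assessment", and the investigator should consult the sponsor. A note classes palliative radiation to the brain, or to a symptomatic solitary lesion, as clinical progression.

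Protocol Section 6.5.3 lists therapies prohibited during screening and treatment. One bullet in that list is a permission: "Prior and concomitant palliative radiation therapy is allowed if the target lesion(s) are not included within the radiation field" and at most 25% of bone marrow is irradiated. It states no other condition and does not point back to 6.5.2. Nor does 6.5.2 point forward to 6.5.3.

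On tumor assessment, Protocol Section 8.1 says: "There will be no formal assessments of efficacy during the rollover study". Section 9.4.1 plans no efficacy analysis.

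**The concern.** Both entries cover radiotherapy given while the participant is on regorafenib in this study, and each reads as a complete permission. An investigator who checks the prohibited list finds an affirmative answer that leaves out the protection against interstitial lung disease (ILD) and the no-PD condition. An investigator who checks the permitted list finds nothing about target lesions.

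Three practical matters depend on which text is followed: whether the lung safeguard is seen, whether a participant with a painful former target lesion may have pain radiotherapy, and what counts as a protocol deviation. The last has some weight because Protocol Section 8 rules out waivers and exemptions, so sites need one rule.

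**Working it through.** The documents give no figure to reproduce. The check is a line-by-line comparison.

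**Step 1. Conditions side by side**

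| Condition | 6.5.2 | 6.5.3 bullet |
|---|---|---|
| Purpose is local pain control | required | not stated |
| Individual benefit-risk assessment | required | not stated |
| No PD, in the investigator's opinion | required | not stated |
| No lung field | required | not stated |
| At most 25% of marrow irradiated | required | required |
| Target lesions outside the field | not stated | required |

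Section 6.5.2 has 5 conditions and 6.5.3 has 2, with 1 in common: 5 + 2 − 1 = 6 distinct conditions. Four are only in 6.5.2 (5 − 1) and one is only in 6.5.3 (2 − 1). The sponsor-consultation rule and the progression note also stand only in 6.5.2. If they are counted as conditions, the 6.5.2-only figure is 4 + 2 = 6. These are counts of text and do not measure risk.

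The time covered differs as well. Section 6.5.2 addresses radiotherapy during the study, while 6.5.3 addresses both prior and concomitant radiotherapy.

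**Step 2. Do the rules give different answers?** Each case below assumes on-study palliative radiotherapy for pain, a benefit-risk assessment done, and the marrow limit met.

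| Case | 6.5.2 alone | 6.5.3 alone | Both together |
|---|---|---|---|
| Field includes lung, spares target lesions, no PD | not allowed | allowed | not allowed |
| Painful bone lesion that was a feeder-study target lesion, not solitary, no lung field, no PD | allowed | not allowed | not allowed |
| Painful non-target bone lesion, not solitary, no lung field, PD in the investigator's opinion | not allowed | allowed | not allowed |

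The two texts disagree in all three cases. The combined reading keeps every safeguard, at the price of barring the second case. Neither section tells the reader to combine them.

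**Step 3. Does another rule supply the missing no-PD condition?** Only in part. Protocol Section 7.1 requires withdrawal for clinical progression, and Section 4.1 lets treatment continue while the physician judges that there is benefit. PD as such is not among the listed withdrawal reasons.

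**Step 4. What does the target-lesion condition serve here?** The term occurs only in the 6.5.3 bullet and is not defined. The Schedule of Activities has 11 procedures: consent, eligibility, demography, tumor type, medical history, study treatment, dispensing, accountability, AE review, SAE review and concomitant medication. None of the 11 assesses lesions. The items that Section 4.1 carries into the rollover eCRF include "demography including study number, tumor type, and participant's identification number of the feeder study" but no lesion data. The condition therefore serves no assessment made in this study. Whether it serves something outside the study is a separate question, taken up in the objection.

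**Step 5. Is any analysis affected?** No. The SAP describes demography, concomitant medication, exposure and adverse events. No analysis set, endpoint or table is defined through either radiotherapy rule.

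**The case against.** The strongest reply is that the two entries sit in adjacent subsections and can both be met. Protocol requirements normally apply cumulatively, and on that reading the lung, no-PD and marrow conditions all hold. An investigator planning radiotherapy would have to overlook a labelled radiotherapy entry in the section just before. Other controls exist too: sponsor consultation if regorafenib continues during radiotherapy, and in Section 6.5.4, "The Medical Monitor should be contacted if there are any questions regarding concomitant or prior therapy". The conflict over a painful target lesion is also narrow. Radiation to a symptomatic solitary lesion or to the brain already counts as clinical progression, which leads to withdrawal under 7.1.

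Most of this stands, and it limits the weight of the point. It does not remove it. A stated permission omits a safety condition set elsewhere in the same protocol, and the Medical Monitor route helps only a site that sees a question to ask.

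Two stronger readings are tempting and are not supported:

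- A reader might infer that the sections contradict each other outright. They do not, since a site can comply with both.
- A reader might infer that the target-lesion condition has no purpose and can simply be deleted. The documents do not show that. The 6.5.3 list covers screening, and the Schedule of Activities notes: "During the screening period the participant will be on treatment under the umbrella of the feeder study". Target lesions may still be followed there. Exclusion criterion 3 ties prohibited medications to the feeder protocol. Section 9 allows pooling with feeder data, Section 10.1.9 allows contribution to feeder publications, and irradiating a followed lesion could influence the judgement of continued benefit under Section 4.1. The feeder protocols cannot be checked here.

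**Conclusion.** The inconsistency is real and minor. It concerns study conduct and patient safety, and worth correcting because a one-bullet change makes the ILD safeguard and the no-PD condition apply to all on-study radiotherapy. Its size in participants cannot be estimated: the documents give no radiotherapy frequency, and SAP Section 4.1 expects few patients.

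The conclusion rests on two readings. First, that concomitant radiotherapy in 6.5.3 includes radiotherapy given during the rollover treatment phase, which the introduction to that list supports. Second, that target lesion, if it has a meaning here, has its feeder-study meaning. The protocol does not say so.

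**What to change.** Replace the radiotherapy bullet in Protocol Section 6.5.3 with:

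> Palliative radiotherapy during the treatment phase other than as permitted in Section 6.5.2.

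The no-PD, 25% marrow and no-lung-field conditions then always apply on study.

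Add a statement that radiotherapy before the first rollover dose follows the feeder protocol, with at most 25% of bone marrow irradiated. This keeps a rule for prior radiotherapy and for the screening period.

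The sponsor should then decide on the target-lesion condition for on-study radiotherapy. If no pooled feeder-study analysis and no judgement of continued benefit needs it, drop it. If one does, move it into the 6.5.2 list and define target lesions as those recorded in the feeder study.

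The cost is one amended bullet and the added statement, with the ethics approval that Section 10.1.1 requires for amendments. No extra data, visits or procedures are needed. The downside is possible loss of the target-lesion restriction, which is why the sponsor's check comes before any deletion.
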